10.0 Statistical Analysis

10.1 Data analysis

Primary goals

- To determine the proportion of patients who have an increase of interferon gamma production within the tumor microenvironment from before and after therapy with the immune checkpoint inhibitor, nivolumab. The change will be dichotomized as increase vs. no increase with the threshold of 4pg/ml. The proportion of the patients with increase will be evaluated by exact binomial test.
- To evaluate the safety of using brain tumor microdialysis to monitor response to immune modulators in patients with recurrent glioblastoma.
 Descriptive statistics, such as frequency and percentage, will be used to evaluate the safety of these procedures.
- To evaluate the safety of the combination of Nivolumab and BMS-986-016 in the treatment of recurrent glioblastoma patients.
 Descriptive statistics, such as frequency and percentage, will be used to evaluate the safety of these treatments.

Exploratory Goals

1) To determine the change in interferon gamma production within the tumor microenvironment and in the rest of the body from before and after therapy with the immune checkpoint inhibitor, nivolumab.

A one-sample t-test or Wilcoxon signed rank test will be performed to evaluate the change (continuous) over time (between pre- and post-treatment) in the outcome measures

2) To evaluate the pathological response of the immune microenvironment of brain tumor tissue to the first dose of Nivolumab

A one-sample t-test or Wilcoxon signed rank test will be performed to evaluate the change between pre- and post-treatment for each marker evaluated.

3) To evaluate the clinical response (progression free survival, overall survival) of recurrent glioblastoma patients to this treatment

The Kaplan-Meier method will be used to estimate the survival function and generate survival curves. The study is not powered to detect significant differences in survival between the patients in this cohort and historical controls.

4) To describe the difference in survival between responders and non-responders Descriptive statistics will be used. The study is not powered to detect significant differences in survival between the patients in this cohort and historical controls. 5) To examine the differences in the immune cells and secreted factors of the tumor environment as compared to the immune cells and secreted factors of the cerebral spinal fluid, blood and potential bone marrow in response to this treatment Repeated measures ANOVA or Friedman test will be performed to evaluate the change (continuous) over time (between pre- and post-treatment) and between brain compartments (or between brain and the peripheral immune system, or between the two different micro dialysis catheters).

10.2 Power analysis

The power analysis was performed using the primary outcome, which is defined as increase vs. no increase based on the difference in expression of interferon gamma between baseline and the 5th day after nivolumab treatment with the threshold of 4pg/ml. The hypothesis is that the proportion of the patients with increase is greater than 0.2. The expected proportion is 0.7. The following table shows the estimated power based on 10 subjects for different null and observed proportions using the two-sided exact binomial test.

Null	Expected	Actual	Estimated
Hypothesis	Proportion	Alpha	Power
0.1	0.9	0.0128	>.999
	0.8	0.0128	>.999
	0.7	0.0128	0.989
	0.6	0.0128	0.945
0.2	0.9	0.00637	0.998
	0.8	0.00637	0.967
	0.7	0.00637	0.85
0.3	0.9	0.01059	0.987
	0.8	0.01059	0.879
0.4	0.9	0.01834	0.930

Table 6 - The estimated power of 10 subjects for different null and observed proportions

Table 6 indicates that a sample size of 10 subjects: (a) will have 85 power to reject the null hypothesis: $p \le 0.2$ when ≥ 7 subjects are found to have increased interferon gamma in five days after the treatment and (b) will have 93.0% power to reject the null hypothesis: $p \le 0.4$ when ≥ 9 subjects are found to have increased interferon gamma.

Observed	95% CL	
proportion		
1	0.6915	1
0.9	0.555	0.9975
0.8	0.4439	0.9748
0.7	0.3475	0.9333 (a)
0.6	0.2624	0.8784
0.5	0.1871	0.8129
0.4	0.1216	0.7376
0.3	0.0667	0.6525

Table 7 - 95% confidence limits (CL) for proportions with a sample size of 10 subjects.

Table 7 presents the 95% confidence limits for the observed binomial proportion 0.3 to 1.0 based on a sample size of 10 subjects. For a sample size of 10 subjects, if 7 subjects are observed with increased interferon gamma in five days, the interval of (0.35, 0.93) will have 95% probability to include the true proportion (a).

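### Section 10.1 does not tie the primary exact binomial test to the design in 10.2, and Table 6 and the sentence below it disagree on whether 6 of 10 rejects the null of 0.2

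*Combined protocol and SAP*

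**What the plan says.** Section 10.1 gives the analysis of the interferon gamma outcome in one line: "The proportion of the patients with increase will be evaluated by exact binomial test". It names no null value, significance level, sidedness or cutoff.

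Section 10.2 supplies some of this:

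- The direction and null: "The hypothesis is that the proportion of the patients with increase is greater than 0.2".
- The planning value: "The expected proportion is 0.7".
- The test behind Table 6, described only as giving power "for different null and observed proportions using the two-sided exact binomial test", with no nominal level and no named construction.
- Table 6, null 0.2: actual alpha 0.00637, with power 0.85, 0.967 and 0.998 at 0.7, 0.8 and 0.9.
- The sentence below Table 6: a power of 85 for rejecting p ≤ 0.2 when at least 7 "subjects are found to have increased interferon gamma in five days after the treatment", and 93.0% for rejecting p ≤ 0.4 when at least 9 do.
- Table 7: 95% limits of 0.1871 to 0.8129 for an observed 0.5, and 0.2624 to 0.8784 for 0.6.

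**The concern.** With 10 patients, one patient more or fewer decides the test, so the cutoff is effectively the analysis. A reader needs the null, the level, the form of the two-sided test and the resulting count in one place. The line in 10.1 has none of these and does not refer to 10.2.

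Two problems follow. First, the only cutoffs written in words (7 and 9) may not be the ones that Table 6 uses. Second, at null 0.2 the binomial is skewed, so different tests that are all properly called two-sided and exact need not agree. At stake is whether the trial's one formal hypothesis test has a single answer fixed before the assay results exist.

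**Working it through.** **Inputs.** n = 10, null 0.2 and planning value 0.7 come from Section 10.2. The nominal level is not stated; I assume two-sided 0.05 because Table 7 uses 95% limits. X is the number of patients with an increase.

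**1. Reproduce Table 6, null 0.2.** An equal-tailed two-sided 0.05 test rejects where either tail probability is at most 0.025.

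- P(X ≥ 5 | 0.2) = 0.0328, above 0.025.
- P(X ≥ 6 | 0.2) = 0.00637, below 0.025.
- P(X = 0 | 0.2) = 0.8^10 = 0.107, above 0.025, so nothing is rejected in the lower tail.

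The region is X ≥ 6. Its actual alpha is 0.00637, and P(X ≥ 6 | 0.7) = 0.850. Both match Table 6.

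**2. Other rows.** The same test gives:

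| Null | Rejects at | Actual alpha |
|---|---|---|
| 0.1 | ≥ 4 | 0.0128 |
| 0.3 | ≥ 7 | 0.01059 |
| 0.4 | 0 or ≥ 8 | 0.00605 + 0.01229 = 0.01834 |

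All agree with Table 6, as do the powers. All of Table 7 reproduces as Clopper-Pearson limits. A minimum-likelihood test at a nominal 0.025 gives the same four regions, so Table 6 fixes the cutoff for null 0.2 without fixing the label of the test.

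**3. The cutoffs in the text.**

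| Rule | Null | Actual alpha | Power | Text says |
|---|---|---|---|---|
| ≥ 6 | 0.2 | 0.00637 | 0.850 at 0.7 | not given |
| ≥ 7 | 0.2 | 0.00086 | 0.650 at 0.7 | 85 |
| 0 or ≥ 8 | 0.4 | 0.01834 | 0.930 at 0.9 | not given |
| ≥ 9 | 0.4 | 0.00168 | 0.736 at 0.9 | 93.0% |

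Both written cutoffs are one patient higher than the rule to which the power belongs.

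**4. How often 6 of 10 arises.** P(X = 6 | 0.7) = 0.8497 − 0.6496 = 0.200. At a true 0.6 it is 0.6331 − 0.3823 = 0.251. Table 6 and Table 7 (lower limit 0.2624) reject 0.2 at this count; the sentence below Table 6 does not.

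**5. A different two-sided construction.** The minimum-likelihood p-value sums all outcomes no more likely under the null than the one observed. At X = 5 no lower-tail outcome qualifies: P(X = 0 | 0.2) = 0.107 exceeds P(X = 5 | 0.2) = 0.0328 − 0.0064 = 0.0264, and counts 1 to 4 are likewise more probable than 5. So p = P(X ≥ 5) = 0.0328, which rejects at 0.05. The doubled-tail p is 2 × 0.0328 = 0.0656, which does not. Rejecting at ≥ 5 has actual alpha 0.033 and power 0.953 at 0.7, against 0.00637 and 0.85 in Table 6. Table 7's interval for 5 of 10 contains 0.2. Exactly 5 of 10 has probability 0.9527 − 0.8497 = 0.103 at a true 0.7.

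**The case against.** A reader might infer that the plan leaves 5 of 10 open, to be settled by whatever software is used. The documents do not support that. Table 6's actual alpha places 5 outside the rejection region, the sentence below it asks for 7, and Table 7's interval for 5 of 10 includes 0.2. All three point to no rejection, and no software is named. A minimum-likelihood test at 0.05 is contradicted by Table 6's own figures. Nor is it right that no alpha appears at all: Table 6 lists an actual alpha for each null, and only the nominal level is missing.

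A second tempting step is to call the two-sided test wrong because the hypothesis is directional. At null 0.2 and n = 10 the equal-tailed 0.05 test has no lower rejection region, so it coincides with a one-sided test at 0.025. Moving to one-sided would also change the null 0.4 alpha from 0.01834 to 0.0123.

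The 7 and 9 may simply be the expected proportions restated as counts (10 × 0.7 and 10 × 0.9). That would explain the slip, but the sentence still reads as a rejection condition and gives it the wrong power.

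Finally, this is a single-arm pilot whose stated primary goal is to determine a proportion, and in the material reviewed no stopping or treatment decision hangs on the p-value. That limits the consequences. It does not settle the verdict at 6 of 10, nor supply the missing link from 10.1 to 10.2.

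**Conclusion.** The point holds as a gap in specification and an internal contradiction. Section 10.1 does not carry over the design rule, and 10.2 gives neither the nominal level nor the two-sided construction. The real conflict is at 6 of 10, where the tables reject and the text does not, with a 20.0% chance of that count at the planning value. The text's rule of 7 or more would have 65.0% power, 20 percentage points below the 85 it claims. The exposure at 5 of 10 is secondary: it arises only if an analyst follows 10.1 alone and uses a test that does not reproduce Table 6.

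This rests on exactly 10 evaluable patients and an assumed nominal two-sided 0.05. The cutoff mismatch does not depend on the second assumption, because the alpha of 0.00637 equals P(X ≥ 6 | 0.2) and the power of 0.85 equals P(X ≥ 6 | 0.7).

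**What to change.** State the same rule in 10.1 and 10.2: null proportion 0.2; equal-tailed exact binomial test at two-sided 0.05, equivalent here to the lower Clopper-Pearson 95% limit exceeding 0.2; reject if at least 6 of 10 patients show an increase; actual alpha 0.0064, power 85% at 0.7.

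In the sentence below Table 6, change 7 to 6 for null 0.2 and 9 to 8 for null 0.4. This has to go in with the rule, or 10.2 would still contradict itself. Tables 6 and 7 then stand unchanged.

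The cost is an edit to two sections, with no extra patients, samples or analyses. Section 4.5.1 has the cytokine samples tested at the conclusion of enrollment, so the edit should be made before those results are available.

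### Section 10.2 ties the stated power to the wrong responder counts: 85% belongs to at least 6 of 10, not 7, and 93.0% to at least 8, not 9

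*Combined protocol and SAP*

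**What the plan says.** Section 10.1 gives the analysis of the interferon gamma outcome in one line: "The proportion of the patients with increase will be evaluated by exact binomial test". It states no null value, alpha, sidedness or rejection count. Both safety outcomes, which are also primary, are descriptive only.

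Section 10.2 supplies the null and the planning value: "The hypothesis is that the proportion of the patients with increase is greater than 0.2", and "The expected proportion is 0.7". It introduces Table 6 as follows: "The following table shows the estimated power based on 10 subjects for different null and observed proportions using the two-sided exact binomial test". Two rows matter most here:

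- null 0.2, expected 0.7: actual alpha 0.00637, power 0.85
- null 0.4, expected 0.9: actual alpha 0.01834, power 0.930

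The sentence under the table then translates these rows into counts. Part (a) attaches a power of 85 (printed without a percent sign) for rejecting p ≤ 0.2 to the case where at least "7 subjects are found to have increased interferon gamma in five days after the treatment". Part (b) says the study "will have 93.0% power to reject the null hypothesis" p ≤ 0.4 when at least "9 subjects are found to have increased interferon gamma".

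**The concern.** With 10 patients, each rejection count has one exact alpha and, for a given true proportion, one exact power. The counts 7 and 9 in the sentence equal ten times the expected proportions 0.7 and 0.9. That suggests the expected number of responders was written down as the rejection threshold. The two are different quantities: with a null as low as 0.2, a test on 10 patients can reject at a count below the expected 7.

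The sentence is also the only text in the plan that links a number of responders to rejecting p ≤ 0.2. A reader looking for the success criterion of the one formally tested primary outcome will find 7. Applied as the rule, 7 does not deliver the stated power, and a result of 6 of 10 would be called differently by the sentence and by the test.

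**Working it through.** **Inputs.** n = 10, a two-sided exact binomial test, nulls 0.1 to 0.4 and expected proportions 0.6 to 0.9, all from section 10.2. The nominal alpha is not stated. I take two-sided 0.05 with 0.025 in each tail, in line with the 95% limits in Table 7.

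**Formula.** For rejection at r or more responders, alpha is P(X ≥ r) under the null proportion, plus any lower-tail region with probability at most 0.025. Power is the probability of the same region under the true proportion. X is binomial with n = 10.

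**Reproducing Table 6.** The smallest r with upper tail at most 0.025 gives:

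| Null | Rejection region | Alpha | Power at true proportion |
|---|---|---|---|
| 0.1 | X ≥ 4 | 0.0128 | 0.9: >.999; 0.8: >.999; 0.7: 0.989; 0.6: 0.945 |
| 0.2 | X ≥ 6 | 0.00637 | 0.9: 0.998; 0.8: 0.967; 0.7: 0.850 |
| 0.3 | X ≥ 7 | 0.01059 | 0.9: 0.987; 0.8: 0.879 |
| 0.4 | X ≥ 8 or X = 0 | 0.01229 + 0.00605 = 0.01834 | 0.9: 0.930 |

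Every printed row is recovered. For null 0.2 there is no lower region, because P(X = 0) = 0.107. For null 0.3 there is none either, because P(X = 0) = 0.028.

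**Testing the counts in the sentence.**

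- *Null 0.2, at least 7.* Alpha is 0.00086. Power at 0.7, 0.8 and 0.9 is 0.650, 0.879 and 0.987, against the printed 0.85, 0.967 and 0.998. None of the three rows matches. The last two values are in fact the null-0.3 rows.
- *Null 0.4, at least 9 (or 0).* Alpha is 0.00168 + 0.00605, which is 0.0077 after rounding. Power at 0.9 is 0.736, against the printed 0.930.

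**Cross-check with Table 7.** The printed lower 95% limit at 6 of 10 is 0.2624, which excludes 0.2. At 5 of 10 it is 0.1871, which does not. At 8 of 10 it is 0.4439, which excludes 0.4. Both tables therefore put the boundaries at 6 and 8.

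**Where the sentence and the test disagree.** For the stated null of 0.2 this is exactly 6 of 10. The upper-tail p is 0.00637; doubled, 0.0127. If the true proportion is 0.7, P(X = 6) = 210 × 0.7⁶ × 0.3⁴ = 0.2001, which is also the difference in power, 0.8497 − 0.6496.

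**The case against.** The best defence is that the sentence is loose rather than miscalculated. The plan describes the same column as both expected and observed proportions. If 7 and 9 are read as true proportions of 0.7 and 0.9 expressed as counts, both powers are right. That probably explains how the sentence arose, but it is not what the sentence says: it speaks of subjects found to have an increase, which is an observed result.

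It can also be said that section 10.2 only justifies the sample size, that nothing makes 7 a formal success criterion, and that an analyst who simply runs the test in 10.1 will reject at 6 of 10. This is true and limits the harm. But 10.1 gives no boundary of its own, so the sentence is the only count a reader can take from the plan.

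Two further points stand as refinements. First, power depends on a true proportion, not on an observed count, so changing the digits alone leaves the sentence badly formed. Second, the 20.0% assumes equal tails, which 10.1 does not state. Under the minimum-likelihood two-sided exact test, 5 of 10 would also reject (p = 0.0328). The disagreement would then cover 5 and 6, with probability 0.9527 − 0.6496 = 0.303 at a true proportion of 0.7. That test does not fit Table 6, since it would give an alpha of 0.0328 for null 0.2 rather than 0.00637. No convention examined leads to 7 or 9.

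**Conclusion.** The concern holds. Table 6, Table 7 and the sample size of 10 are right; the sentence interpreting Table 6 is wrong in both parts. For the stated hypothesis (null 0.2, true proportion 0.7), 85.0% power goes with at least 6 of 10, and the printed count of 7 would give 65.0%. For null 0.4 and true proportion 0.9, 93.0% goes with at least 8 of 10, and the printed count of 9 would give 73.6%. This second part is illustrative, since the study's hypothesis uses 0.2.

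The practical consequence is confined to a result of exactly 6 of 10, given the equal-tailed test at 0.025 per tail that both tables imply. An analyst who runs that test and ignores the sentence would reach the right conclusion.

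**What to change.** In section 10.2, replace 7 with 6 and 9 with 8, and state the true proportion beside each power: 85% power if the true proportion is 0.7, rejecting p ≤ 0.2 at 6 or more of 10; 93.0% power if it is 0.9, rejecting p ≤ 0.4 at 8 or more. If 7 and 9 are really the intended thresholds, keep them and restate the powers as 65.0% and 73.6%.

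In section 10.1, add one sentence naming the equal-tailed exact binomial test at 0.025 per tail. If the cutoff is corrected to 6, say there that it rejects p ≤ 0.2 at 6 or more of 10. This also settles whether 5 of 10 could count.

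The cost is a corrected sentence in 10.2 and one added sentence in 10.1. Tables, sample size and conduct do not change. Section 4.5.1 has the samples sent for cytokine testing at the end of enrollment, so the correction should be made before those results are seen.

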11.0 Human Subjects Protection

11.1 Subject Selection

Enrollment will be equitable among those individuals who meet the inclusion criteria and will not be based on race, ethnicity, or gender.

Patients who are considered for this protocol are those with recurrent glioblastoma who are surgical candidates. The patient population for this study is restricted to patients with recurrent glioblastoma, as experimental therapy is warranted in the care of these patients and surgical resection is indicated for these patients.

11.2 Justification for exclusion of participants less than 18 years old

Participants under the age of 18 years are excluded because glioblastoma is rarely seen in the younger population. An adult's immune system is also different so the effects of immune modulators in children and young adults may also be different than in adults.

11.3 Justification for exclusion of other vulnerable subjects

Subjects who lack consent capacity due to cognitive impairment, or patients with mental disorders or with cognitive impairment that renders them unable to give consent will be excluded because they will be unlikely to be able to safely participate in ongoing microdialysis monitoring in the intensive care unit.

Subjects who do not speak English or Spanish will be excluded from the protocol, as there is a need for close communication between the investigators and subjects, given the nature of the interventions in this trial. Pregnant and breastfeeding women are excluded as we do not know if Nivolumab can harm a developing fetus or breastfeeding infant.

11.4 Safeguards for vulnerable populations and sensitive procedures

Adults who participate in the protocol are required to sign a durable power of attorney because of the possibility that they may become unable to make decisions about research participation and medical care during the course of participation.

If a patient loses consent capacity after enrollment but before completion of the monitoring period in the inpatient unit and the subsequent tumor resection, they will proceed through the trial, granted that the patient opts to sign assent and their durable power of attorney believes that they would want to proceed. If a patient loses capacity after enrollment but before completion of the monitoring period in the inpatient unit and refuses to sign the assent or the durable power of attorney determines that the patient would not want to continue with the trial, they are removed from the trial and replaced. Those who lose capacity after enrollment and after completion of the monitoring period and subsequent tumor resection will be given the opportunity to continue in the study. In this latter case, a memorandum will be generated that includes a justification for their continued involvement in the protocol, and their DPA will be referred to for further decision-making while at the National Institutes of Health.

The decision process discussed with the DPA will include a summary of risks of the research and likelihood of benefit (if any) for adults unable to consent. The procedure utilized for obtaining the surrogate consent (assent) will be documented, including the procedures for allowing dissent.

The Ability to Consent Assessment Team (ACAT) will be used to provide additional safeguards and protections for vulnerable subjects. If there are any questions about capacity to consent, the Ability to Consent Assessment Team (ACAT) may be consulted. The ACAT may also be consulted, at the discretion of the PI on an ad hoc basis if the subject's mentation changes over the course of the study.

Safeguards for females of childbearing potential: Pregnant women may not be enrolled in this trial. Pregnancy testing will be performed during the initial screening portion of the trial, and every month, prior to MRI scanning, subsequently; and contraception is required during the duration of the trial. Contraception is also required for the 24 weeks after the last exposure to the study drug for those patients of childbearing potential. Subjects who are capable of fathering children will need to use effective contraception until 33 weeks after the last exposure to the study drug.

Safeguards for pediatric patients: Pediatric patients will not be enrolled in this trial.

Safeguards for NIH employees: Protections for employees and staff participating in this study include 1) assuring that the participation or refusal to participate will have no effect, either beneficial or adverse, on the subject's employment or position at the NIH,

2) giving employees and staff who are interested in participating the "NIH Information Sheet on Employee Research Participation" prior to obtaining consent, and 3) assuring that there will be no direct solicitation of employees or staff. 4) Independent consent monitoring will be provided by the NIH HSPU. 5) The PI will train study staff regarding obtaining and handling potentially sensitive and private information about co-workers through staff discussions and written branch/section procedures. No compensation will be provided for this protocol.

Sensitive information will be collected from employees participating in the study, including pregnancy status, full medical history, family medical history, psychiatric history, substance abuse history and other components of a full medical history. Surgical treatment will require the employee to be disrobed in front of other clinical center staff. These sensitive procedures will be disclosed to employees at the time of enrollment. Sensitive information that is made part of the medical record will be accessible to the NIH staff that are involved in the medical care of the patient. Whenever possible, only coded data will be made available to those research staff involved in data processing, and protected health information will only be shared as needed to match patient data to other clinical data for processing.

Safeguards for subjects who do not speak English: Subjects who speak Spanish as their primary language will be given the option of reading and signing the Spanish consent for this protocol. A Spanish interpreter will be used to maximize communication between the investigators and participants during the consent process and to help the investigators answer participant questions. An interpreter will be used for all procedures for those subjects who do not understand English fluently. If a Spanish interpreter is not available, Spanish-speaking staff or the interpreter phone line will be used. An interpreter will also be available throughout the duration of the study and at any follow-up appointments for all patients.

Sensitive procedures: No sensitive procedures (deception, placebo, medication withdrawal, etc.) will be used.

